#### **6.5.1. Prohibited Interventions**

There are no prohibited drug classes in this study. However, some drugs, eg, GLP-1 agonists, pramlintide or opioid drugs, may slow GE and may be undesirable in participants with DG.

Relamorelin

**6.5.2. Permitted Interventions**

Any medication or vaccine (including over-the-counter or prescription medicines, vitamins, and/or herbal supplements) that the participant is receiving during the study must be recorded on the eCRF along with:

- Indication
- Dates of administration including start and end dates
- Dosage information including dose and frequency

DG participants enrolled in this study will consist mostly of participants receiving 1 or more prescription medications for blood-glucose control, as needed. Good clinical practice allows for frequent adjustment of medication by participants and their health care providers to minimize large fluctuations in glycemia, and this practice is encouraged in this study. Certain diabetic drugs delay GE and are not expected to benefit participants with DG. Other therapy considered necessary for the participant's welfare may be given at the discretion of the investigator or participant's health care provider.

The sponsor or designee is to be contacted if there are any questions regarding concomitant therapy.

**6.5.3. Rescue Medicine**

There is no restriction on the use of medications to alleviate symptoms of DG such as nausea and vomiting. The use of such treatment and its frequency are to be recorded on the concomitant medications eCRF.

**6.6. Dose Modification**

No dose modifications are planned.

**6.7. Intervention after the End of the Study**

No interventions are planned after closure of the study.

Relamorelin

**7. Discontinuation of Study Intervention and Participant Discontinuation/Withdrawal**

A premature discontinuation will occur if a participant who signs the ICF and is dosed with study intervention ceases participation in the study, regardless of circumstances, before the completion of the protocol-defined study procedures.

Definitions of the standard terms that may lead to discontinuations are provided in [Appendix 5](#).

Reasons for discontinuation from the study intervention and/or the study may include the following commonly used or other acceptable terms:

Commonly Used Terms	Other Acceptable Terms
Adverse event Completed Lack of efficacy Lost to follow-up Other Physician decision Pregnancy Protocol deviation Site terminated by sponsor Study terminated by sponsor Withdrawal by subject	Death Disease relapse Failure to meet entry criteria Progressive disease Technical problems

**7.1. Discontinuation of Study Intervention**

**7.1.1. Temporary Discontinuation**

In the event of AE or intercurrent illness, dosing of study intervention can be stopped temporarily for a maximum duration of 14 days. If longer cessation of dosing is necessary, the investigator must contact the sponsor.

Relamorelin

### 7.1.2. Permanent Discontinuation

Permanent discontinuation of study intervention also requires discontinuation from the study. The following criteria should be evaluated:

- Special consideration should be paid to the appearance of abnormal laboratory test results suggesting severe drug-induced liver injury (DILI). Discontinuation of study intervention for abnormal liver function should be considered by the investigator when a participant meets criteria for Hy's law (see Section 8.3.7.1 and Appendix 9) or if the investigator believes that it is in the best interest of the participant.
- Documented episode of diabetic ketoacidosis, hyperosmolar non-ketotic diabetic syndrome, or severe hypoglycemia (defined as glucose levels < 3mmol/L, or < 54 mg/dl) that are assessed as study treatment-related.
- Female participants who become pregnant during the study must be discontinued from study intervention immediately and withdrawn from the study. See Appendix 7 for further details regarding follow-up of the participant through the pregnancy.

See the SoA (Section 1.3) for data to be collected at the time of study intervention discontinuation.

### 7.2. Participant Discontinuation/Withdrawal from the Study

- A participant may withdraw from the study at any time at his/her own request or may be withdrawn at any time at the discretion of the investigator for safety, behavioral, compliance, or administrative reasons.
- If the participant withdraws consent for disclosure of future information, the sponsor may retain and continue to use any data collected before such a withdrawal of consent.
- If a participant withdraws from the study, he/she may request destruction of any samples taken and not tested, and the investigator must document this in the site study records.
- See the SoA for data to be collected at the time of study discontinuation and follow-up and for any further evaluations that need to be completed.

Relamorelin

### 7.3. Lost to Follow-Up

A participant will be considered lost to follow-up if he or she repeatedly fails to return for scheduled visits and is unable to be contacted by the study site.

The following actions must be taken if a participant fails to return to the clinic for a required study visit:

- The site must attempt to contact the participant and reschedule the missed visit as soon as possible and counsel the participant on the importance of maintaining the assigned visit schedule and ascertain whether or not the participant wishes to and/or ought to continue in the study.
- Before a participant is deemed lost to follow-up, the investigator or designee must make every effort to regain contact with the participant (where possible, 3 telephone calls and, if necessary, a certified letter to the participant's last known mailing address or local equivalent methods). These contact attempts will be documented in the participant's medical record.
- If the participant continues to be unreachable, he/she will be considered to have withdrawn from the study with a primary reason of lost to follow-up.

## 8. Study Assessments and Procedures

Scheduled evaluations and laboratory tests (serum chemistries and hematologic assessments, including HbA1c and pregnancy testing) for each participant will be performed as noted in the SoA (refer to Section 1.3).

A central laboratory will be used for safety laboratory assessments. Safety data as well as central laboratory results will be collected as noted in the SoA.

- Study procedures and their timing are summarized in the SoA (Section 1.3).
- Protocol waivers or exemptions are not allowed.
- Immediate safety concerns are to be discussed with the sponsor immediately upon occurrence or awareness to determine if the participant will continue or discontinue study intervention.

## Relamorelin

- Adherence to the study design requirements, including those specified in the SoA, is essential and required for study conduct.
- The maximum amount of blood collected from each participant over the duration of the study, including any extra assessments that may be required, will be approximately 170 mL. Repeat or unscheduled samples may be taken for safety reasons or for technical issues with the samples.

All participants who roll over to this continued-access study (Study 3071-305-020) after completing their final visit assessments in either Study RLM-MD-03 or Study RLM-MD-04 are required to sign a new IC. Additionally, eligible participants who completed these studies prior to administrative initiation of this protocol at their study center, will be allowed to participate in this continued-access study, but are required to sign a new IC. Information from the final visit of Study RLM-MD-03 or Study RLM-MD-04 will be used as the information for Visit 1 (Baseline) of this study for these participants; if a participant enters this continued-access study > 30 days after last visit in lead-in study, Visit 1 baseline assessments will be completed (See SoA, Section 1.3). Demography and ongoing medical history will also be rolled over from Studies RLM-MD-03 or RLM-MD-04.

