## Relamorelin

management of blood glucose for both T1DM and T2DM patients due to carbohydrates being delivered to and therefore absorbed from the small intestine at variable times after ingestion. As a result, diabetic patients with DG often have poorly controlled diabetes, frequently with alternating hypo- and hyperglycemia, especially if treated with insulin.

The PD effect of RLM on gastric emptying was confirmed, and the beneficial effects on the symptoms of DG were observed in the Phase 2b study, RM-131-009. Efficacy, safety, and tolerability of RLM are under investigation in Phase 3 studies, including long-term efficacy and safety studies conducted for up to 12 months' duration.

A significant unmet medical need exists for a safe and effective treatment of patients with DG whose quality of life is negatively impacted by their disease and for whom the current standard of care is suboptimal. While waiting for regulatory assessment of the results in the Phase 3 studies, the sponsor is planning to provide access to RLM to participants with DG who have completed double-blind treatment in the Phase 3 program (Studies RLM-MD-03 and RLM-MD-04).

The objective of Study 3071-305-020 is to assess the safety of RLM in participants with DG who have previously completed the Phase 3 studies, RLM-MD-03 or RLM-MD-04. Safety assessments include AEs, clinical laboratory values, vital signs, and ECGs (reported as clinically significant AEs). No endpoints were specified for this study.

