### 4. Study Design

#### 4.1. Overall Design

Study 3071-305-020 is an open-label, multicenter, multinational safety study in participants with DG who completed the Phase 3 studies, RLM-MD-03 or RLM-MD-04, and have no ongoing AEs from either lead-in study that, in the investigator’s opinion, would preclude participation. Participants who discontinued Studies RLM-MD-03 or RLM-MD-04 for any reason are not to be enrolled into this study. Participants who roll over to this continued access study within 30 days (ie, ≤ 30 days) of completing their final visit assessments in either Study RLM-MD-03 or Study RLM-MD-04 do not need to complete baseline assessments; information from the final visit of Studies RLM-MD-03 or RLM-MD-04 will be used as the information for Visit 1 of this study (see Section 8). Visit 1 should occur in ≤ 30 days of the last visit of the lead-in study. If a participant enters this continued-access study > 30 days after last visit in either lead-in study, Visit 1 baseline assessments will be completed as shown in Section 1.3

Approximately 1000 participants may roll over from Studies RLM-MD-03 or RLM-MD-04 at approximately 700 sites with an anticipated attrition rate of approximately 20% per year. No participant replacement is planned in this continued-access, open-label study.

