#### 9.4.1.2. Clinical Laboratory Assessments

Descriptive statistics for clinical laboratory values (in SI units) at baseline and changes from baseline at each assessment will be presented for each clinical laboratory assessment.

The criteria for PCS laboratory values will be detailed in the SAP. The number and percentage of participants who have PCS postbaseline clinical laboratory values will be tabulated at each assessment. The percentages will be calculated relative to the number of participants who have available non-PCS baseline values and at least 1 postbaseline assessment. The numerator will be

Relamorelin

the total number of participants with at least 1 PCS postbaseline value. A supportive listing of participants with PCS postbaseline values will be provided for the safety population.

Shift tables from baseline to end of study for clinical laboratory parameters will be presented.

Study-specific assessments (eg, HbA1c) will be summarized as part of the overall clinical laboratory assessments.

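### For entry within 30 days, the only HbA1c baseline the protocol fixes is the lead-in final visit, which is probably on-drug for prior-RLM participants and pre-RLM for prior-placebo participants

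*Protocol*

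**What the plan says.** **Baseline.** Sections 1.1 and 4.1 waive new baseline assessments for participants who roll over within 30 days. Section 4.1 says that "information from the final visit of Studies RLM-MD-03 or RLM-MD-04 will be used as the information for Visit 1 of this study", and Section 8 labels that visit explicitly as Baseline: "Information from the final visit of Study RLM-MD-03 or Study RLM-MD-04 will be used as the information for Visit 1 (Baseline) of this study". The exception is late entry: "if a participant enters this continued-access study > 30 days after last visit in lead-in study, Visit 1 baseline assessments will be completed".

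**Laboratory analysis.** Section 9.4.1.2 says that "changes from baseline at each assessment will be presented for each clinical laboratory assessment". It adds shift tables from baseline to end of study, and PCS percentages among those "who have available non-PCS baseline values and at least 1 postbaseline assessment". HbA1c follows the same rule: "Study-specific assessments (eg, HbA1c) will be summarized as part of the overall clinical laboratory assessments". Section 9.4.1.2 defers the PCS criteria to the SAP but does not defer the choice of baseline. The statistical section names no second baseline and no split by lead-in treatment.

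**Purpose.** The objective in Section 3 is the safety of continued RLM treatment. Section 4.2 goes further and says the study will give enough long-term safety information to support RLM as a chronic treatment. Section 2.3 names worsening glycemic control as a potential risk.

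**The concern.** One label, Baseline, covers two exposure states. A participant who had RLM in the lead-in probably brings an on-drug HbA1c value into the extension. A participant who had placebo brings a value from before any RLM in this program. Change from entry then answers different questions: further change on continued treatment in the first group, and change on first exposure in the second.

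What is at stake is how the glycemic results are read. In prior-RLM participants a mean HbA1c change near zero means no further change, but it could be taken as no effect of RLM. The PCS table has a related gap: a participant whose value became PCS on lead-in RLM and was still PCS at the final visit is not in the denominator. Both matter because the protocol itself identifies glycemic control as the area of risk.

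**Working it through.** The protocol has no sample size calculation, alpha or power (Sections 9.1 and 9.2), so there is no planned figure to reproduce. The check sets the passages side by side and adds an illustration.

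**Step 1: is the baseline likely to be on-drug?**
- Participants come from completed double-blind treatment (Section 2.1) in placebo-controlled studies (Section 4.2), so some had RLM and some had placebo.
- The lead-in dose equals the extension dose (Section 4.3).
- The protocol does not say when the last lead-in dose falls relative to the final visit. On-drug is therefore probable, not stated.

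**Step 2: would the HbA1c rise already be in it?**
- Section 2.2: HbA1c trended upward after RLM was started and changed little after about 8 weeks.
- Section 4.3: after 12 weeks in the Phase 2b study, the rise at the two higher doses was about twice that at 10 µg BID, so some rise is described at the study dose. It was not seen at 4 weeks in the Phase 2a study. Variability was high.
- Section 2.1 describes the Phase 3 program as "including long-term efficacy and safety studies conducted for up to 12 months". The length of each lead-in study is not given. At the 12-month ceiling, the time to plateau is 8/52 = 0.15 of the treatment period.
- If a lead-in study ran beyond about 8 weeks, most of the rise would precede the extension baseline in prior-RLM participants.

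**Step 3: illustration only.** None of these three quantities is in the protocol:
- D = HbA1c rise on starting RLM, taken as constant
- f = fraction of D reached by the lead-in final visit
- r = share of early entrants who had RLM in the lead-in

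RLM to RLM, change from entry = (1 − f)D. Placebo to RLM, change from entry = D. If the groups were combined, mean change = (1 − r)D + r(1 − f)D = (1 − r·f)D.

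| f | RLM to RLM | Combined, r = 0.50 |
|---|---|---|
| 0.5 | 0.50D | 0.75D |
| 0.8 | 0.20D | 0.60D |
| 1.0 | 0 | 0.50D |

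Over r = 0.33 to 0.75 and f = 0.5 to 1, the combined mean runs from (1 − 0.75 × 1)D = 0.25D to (1 − 0.33 × 0.5)D = 0.835D. Change from the last pre-RLM value would be D in every row. If the effect had washed out fully before the final visit (f = 0), change from entry would also be D and the difficulty would vanish.

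**The case against.** The strongest reply is that nothing here is an error. A change-from-entry summary measures change from entry, which is what a continued-treatment objective asks for. Section 9.4 is a summary, Section 9.4.1 leaves full definition of the safety analysis to the SAP, and a split by prior treatment or a supplementary baseline could be added there. Section 4.2 assigns the placebo-controlled safety comparison to the Phase 3 studies. A pre-RLM comparison in the extension would be uncontrolled and affected by the adjustment of diabetic medication that Section 6.5 expects. The protocol also has safeguards: the change tables show baseline and postbaseline values (Section 9.4), the PCS listing covers the safety population (Section 9.4.1.2), and inadequate diabetes control is an event of special interest (Section 10.3.1).

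Much of this stands. The entry baseline is valid and should stay. The evidence for the HbA1c rise is Phase 2 trends in some participants. What does not fall away is that the protocol itself fixes the baseline and applies it to HbA1c, and that none of the safeguards supplies the pre-RLM value.

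Several stronger readings are tempting but unsupported:
- That the two lead-in groups will be pooled without distinction. The protocol does not say.
- That HbA1c change is understated by a known amount. No input for such a figure is given.
- That all laboratory tests are affected. A drug effect is described only for HbA1c and fasting glucose.
- That late entrants are affected in the same way. They have new Visit 1 assessments.
- That adverse event counts share the gap. This depends on whether the first dose of study intervention means the first open-label dose, and events that began earlier would be in the lead-in data. It is not part of this point.

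**Conclusion.** The point holds as a limit on interpretation, not as a contradiction or a wrong baseline. For entry within 30 days, laboratory change, shifts and the PCS denominator rest on a value that is probably on-drug in prior-RLM participants and pre-RLM in prior-placebo participants. In the first group the HbA1c summary can show further change only, and values already PCS at the lead-in final visit leave the PCS percentage. Alone, that does not carry the chronic-use claim in Section 4.2 for a named glycemic risk.

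No bias size and no headcount is claimed. The conclusion assumes that the lead-in final visit falls on or close to treatment and that lead-in treatment lasted long enough for most of the HbA1c rise to appear. It also assumes that the Phase 2 pattern carries over. Whether HbA1c will have a PCS criterion is left to the SAP. Confidence is medium, and the change is a low-cost improvement worth making.

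**What to change.** In Section 9.4.1, carried into the SAP:

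1. Keep the extension-entry baseline for change during continued treatment.
2. Present laboratory change, shift and PCS summaries by lead-in treatment (placebo to RLM; RLM to RLM) and in total.
3. For HbA1c and glucose only, add a supplementary summary from the last value before RLM was started in the Phase 3 program: the lead-in pretreatment value for RLM to RLM, and the entry baseline for placebo to RLM.
4. Label the supplementary summary as descriptive. It is uncontrolled and influenced by changes in diabetic medication, so it describes change since starting RLM and does not prove a drug effect.

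The cost is a few more tables and a merge of lead-in treatment codes with pretreatment HbA1c and glucose values, which the sponsor should already hold. The codes must be available at analysis. No new data collection is needed.

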### 8.1. Efficacy Assessments

No efficacy assessments are planned for this continued-access study.

### 8.2. Safety Assessments

Safety assessments will include vital signs, clinical laboratory tests (hematology, clinical chemistry including HbA1c, urinalysis), and ECG values reported as clinically significant AEs.

AEs, including SAEs, SUSARs, and study-intervention discontinuation due to AEs will be assessed.

Planned timepoints for all safety assessments are provided in the SoA (Section 1.3).

Relamorelin

**8.2.1. Physical Examinations**

- Physical examinations (as per the investigator's standard of care) are to be performed at baseline, at each annual visit, and at the Final Visit. Symptom-directed (abbreviated) physical examinations, including evaluation of the injection sites for clinically significant reactions, may be conducted as required at other study visits. A clinically significant injection site reaction is to be reported as an AE.
- Any abnormality noted on the physical examination done at Final Study Visit or the Early Termination Visit that was not present on the physical examination at baseline is to be reported as an AE if considered by the investigator to be clinically significant.
- Investigators are to pay special attention to clinical signs related to previous serious illnesses.

**8.2.2. Vital Signs**

Vital signs will be assessed as follows:

- Systolic and diastolic BP, HR, temperature, and respiratory rate will be assessed at baseline, at each annual visit, and at the Final/Early Termination Visit; BP and HR will be assessed at all other visits; the method for measuring temperature will be per the site's preference.
- BP and HR measurements will be assessed in the sitting position with a completely automated device. Manual techniques will be used only if an automated device is not available.
- BP and HR measurements are to be preceded by at least 3 minutes of rest for the participant in a quiet setting without distractions (eg, television, cell phones).
- Vital signs are to be taken before blood collection for laboratory tests.

Relamorelin

### 8.2.3. Electrocardiograms

- Single 12-lead ECG will be obtained at baseline from a lead-in study, at Week 2 (Visit 1a), yearly starting at Visit 5 (Month 12), and at the Final Visit. If a participant enters the continued-access study > 30 days after last visit in lead-in study, an ECG will be obtained at Visit 1 as part of the baseline assessments for the continued-access study. All participants will have an ECG at Week 2 (Visit 1a). If a participant continues in the study for longer than 1 year, ECGs are to be performed annually starting at Visit 5. Any clinically significant changes in ECG results should be reported as AEs.

### 8.2.4. Clinical Safety Laboratory Assessments

- See [Appendix 2](#) for the list of laboratory tests to be performed and the SoA (Section 1.3) for the timing and frequency.
- The investigator must review the laboratory report, document this review, and record any clinically significant changes occurring during the study in the AE eCRF. The laboratory reports must be filed with the source documents. Clinically significant abnormal laboratory findings are those which are not associated with the underlying disease, unless judged by the investigator to be more severe than expected for the participant's condition.
- All laboratory tests with abnormal values considered clinically significant during participation in the study or within 30 days after the last dose of study intervention must be repeated until the values return to normal or baseline or are no longer considered clinically significant by the investigator or MSP.
  - If such values do not return to normal/baseline within a period of time judged reasonable by the investigator, the etiology is to be identified and the sponsor notified.
  - All protocol-required laboratory assessments, as defined in [Appendix 2](#), must be conducted in accordance with the laboratory manual and the SoA (Section 1.3).
  - If laboratory values from non-protocol specified laboratory assessments performed at the institution's local laboratory require a change in participant management or are considered clinically significant by the investigator, then the results must be recorded in the eCRF as AEs/SAEs.
  - Urine dipstick kits are to be used to conduct pregnancy tests.

Relamorelin

